8.6.9. Disease-related Events (DREs) and/or Disease-related Outcomes not qualifying as AEs or SAEs

These events may refer to disease- or complication-related events that are common in Covid-19 patients and can be serious/life-threatening.

They are reported systematically on the eCRF in the pre-defined daily data sections. However, they will NOT be reported as SAE in the eCRF, even though the event may meet the definition of an SAE, unless the investigator considered that there is a reasonable possibility that the study intervention (blinded investigational agent/placebo or study-supplied SoC treatment) caused the event.

These events may occur during the initial hospitalization, lead to a re-admission, or occur in a later hospitalization during follow-up.

The DREs are given in Section 10.4 Appendix 4.

Some of these events can be recorded as AESI, depending on the IMP profile.

8.6.10. Solicited and unsolicited AEs (applicable for injectable IMPs)

- Injectable drugs are associated with a number of well-characterized reactions referred to as ‘solicited adverse events’ (see Appendix 3), including local and systemic manifestations.
- By opposition, unsolicited AE represents signs and symptoms outside the pre-defined checklist reported by the participant/participant’s legally authorized representative.
- Further details on handling of solicited and unsolicited AEs will be given in investigator-specific subprotocol.

8.6.11. Adverse Events of Special Interest (AESI)

Some adverse events of special interest (AESIs) are monitored for after administration of IMPs and require an immediate notification to sponsor. All participants enrolled in the study will be monitored for AESIs for the entire follow-up period. The occurrence of any of these adverse events has to be sent by the investigator to the sponsor immediately and no later than 24h after being aware of it using the SAE form.

Details will be given in the intervention-specific sub-protocol if applicable.

8.6.12. Potentially relevant risks of the research procedures and IMP, and management guidelines in case of Adverse Event

Part to be updated based on information provided by marketing authorization holders regarding the safety language of AE management, for the guidelines that cannot be captured in the specific risk/benefit assessments of the intervention-specific sub-protocol and 6.5 sections.

8.7. Pharmacokinetics

Details will be given in the specific sub-protocols if applicable.

8.8. Genetics

Genetic analyses are not planned in the core platform. If genetic analyses are relevant and indicated for a particular IMP, details on sample collection, storage and analyses will be detailed in the IMP-specific sub-protocol, and in that case, this will be specified in the informed consent form.

8.9. Immunogenicity Assessments

Immunogenicity is not evaluated in this study but could be included in IMP-specific sub protocols if indicated.

8.10. Medical Resource Utilization and Health Economics Parameters

Medical resource utilization and health economic parameters are not evaluated in this study.

9. Statistical Considerations

The statistical analysis plan will be finalized prior to database lock and will include a more technical and detailed description of the statistical analyses described in this section. This section is a summary of the planned statistical analyses of the most important endpoints including primary and key secondary endpoints.

9.1. Statistical Hypotheses

This master protocol opens for testing a wide range of hypotheses, including superiority and non-inferiority. The primary phase 3 trial objective includes demonstrating that study intervention is superior or non-inferior to concurrent comparator in achieving disease progression-free at day 15 for EU-SolidAct Part A, death at day 61 for EU-SolidAct Part B.

For phase 2 trials the primary objective includes exploring if the study intervention is superior to concurrent control on respiratory dysfunction as measured by the SF-ratio at day 5.

Non-inferiority hypotheses will generally not be tested because most explorative trials will want to focus on superiority at least as the primary hypothesis.

In the case of non-inferiority testing, we set the default non-inferiority margin at 3% risk difference both for Part A (occurrence of disease progression) and B (occurrence of death). The argument for this is that a relative risk reduction of 0.8 (lower bound of the confidence interval) is in the Solidarity trial⁵ enough to claim no clinically relevant effect of remdesivir and lopinavir on mortality. With an assumed overall rate of 15%, a 0.8 relative risk reduction corresponds to 3% absolute risk reduction. The final margin will be specified in the intervention-specific sub-protocol in case a non-inferiority hypothesis is tested.

EU-SolidAct Part A (Phase 3)	EU-SolidAct Part B (Phase 3)	EU-SolidAct (Phase 2)
Null superiority hypothesis: Intervention is not different from concurrent control on occurrence of disease progression at day 14.	Null superiority hypothesis: Intervention is not different from concurrent control on occurrence of death at day 60.	Null superiority hypothesis: Intervention is not different from concurrent control on respiratory dysfunction as measured by the SF-ratio at day 5.
Null non-inferiority hypothesis: The difference in occurrence of disease progression at day 14 is at least 3% in favour of concurrent control.	Null non-inferiority hypothesis: The difference in occurrence of disease progression at day 14 is at least 3% in favour of concurrent control.	NA

Superiority

H0: $\pi_A = \pi_B$ against Ha: $\pi_A \neq \pi_B$

where π_A and π_B are the probability of primary endpoint occurrence when treated with the intervention therapy (A) or concurrent control (B).

Operationally the hypotheses will be evaluated by 2-sided tests.

Non-inferiority

H0: $\pi_A - \pi_B \geq 0.03$ against Ha: $\pi_A - \pi_B < 0.03$

Operationally the hypothesis will be evaluated by the two-sided 95% confidence interval with non-inferiority claimed if the interval excludes a 3% difference in favour of the concurrent control treatment.

9.1.1. Multiplicity adjustment for multiple arms

The present study is a multi-arm study with multiple experimental treatment arms and a single control arm. As experimental arms are put together in a single study, because of logistical reasons, no multiplicity adjustment is required.

9.2. Analysis Sets

For the purposes of analysis, the following analysis sets are defined:

Participant Analysis Set	Description
Full analysis set	
 All randomized participants. Participants will be included in the analyses according to the planned randomized intervention.
Safety analysis set	
 All participants who are exposed to a study intervention. Participants will be analysed according to the intervention they actually received.

The full analysis set is used to analyse endpoints related to the efficacy objectives and the safety analysis set is used to analyse the endpoints and assessments related to safety.

The following data points sets are defined:

Defined Data Points Sets	Description
DPS1	
 All observed data will be included in the analysis set.

Defined Data Points Sets	Description
DPS2	
 For participants who discontinue study intervention and/or receive rescue therapy, post-discontinuation or post-rescue observations will not be included.

Full analysis set and DPS1 are used to estimate the primary endpoints and the secondary endpoints for secondary core objective.

Full analysis set and DPS2 are used to for sensitivity analyses.

Safety analysis set and DPS1 are used to present safety data.

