- The control treatment for superiority trials will be the SoC at the local hospital defined as the best available treatment according to local hospital guidelines. The SoC might change as new treatment evidence emerges. Use of new treatment as part of SoC will be captured in the trial database.
- Placebo plus SoC might be considered as control treatment if available, otherwise open-label SoC will be given against open-label intervention. This will be detailed in the intervention-specific protocol.
- If components of SoC are contraindicated with the study intervention(s), we might consider head-to-head comparisons between the study intervention(s) and the SoC component, either to assess or confirm superiority or non-inferiority. This will be detailed in the intervention-specific protocol.
- Current SoC should include the use of dexamethasone 6 mg/day for 10 days in severe or critically ill patients (Part B). Duration and dose could change according to emerging evidence. Other doses or frequencies might be used at the discretion of the treating physician based on clinical judgement.

4.1.1. Randomization:

Participants in EU-SolidAct will randomly be assigned in an equal ratio between the comparator treatment arm(s) and the available active treatment(s) for which the participant is eligible. Over time, it is expected that SoC will evolve. Thus, randomization will be aligned with the current clinical situation and the incremental effects of the study treatment(s) will be appropriately assessed. The randomization will be stratified as described in section 6.3.

In the case of both open-label and blinded investigations in the same part, participants are still randomly assigned in an equal ratio between the arms they are eligible for. In the example figure below with a participant eligible for all five arms in Part B, first the participant is allocated to either investigation B1 or B2 in a 2:3 ratio, and then to either Active 1 or Placebo 1 in a 1:1 ratio or to Active 2, Active 3 or open-label SoC in a 1:1:1 ratio.

[figure not shown]

Figure 4.1 Randomisation illustration

4.1.2. Comparison(s):

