Similarly, assuming a 15% mortality for the SoC group in Part B and a 2-sided type-1 error rate of 5% and using the Log-Rank test, the study will have over 90% power with a sample size of 924, 521 and 378 per arm to detect a treatment difference of 5%, 6.5% and 7.5% respectively. We hypothesize that a treatment difference in mortality rates at day 61 of 5% seems achievable. Therefore, we plan to enrol 950 participants per arm, considering potential drop-outs before the assessment of the primary endpoint at day 61

Table 9.3: Sample size calculation in EU-SolidAct Part B superiority trial

	Scenario 1	Scenario 2	Scenario 3
Outcome (Death at day 61)			
Hypothesized event rate with SoC	15%	15%	15%
Expected event rate with intervention	10%	8.5%	7.5%
Type I error (two-sided)	0.05	0.05	0.05
Power	90%	90%	90%
Hazard ratio (HR)	0.648	0.547	0.48
N per group	924	521	378
Total number of events required	224	115	78

In case combination therapies are assessed by factorial design, the main assumption will be that no interaction exists between the treatments and therefore no modification of the sample size will be necessary. If synergies or effect modifications between treatments are of interest, the intervention-specific sub-protocols will define the sample size needed for detecting the interaction effect.

For a non-inferiority trial, assuming a 15% primary endpoint rate (progression in Part A and mortality in part B) in the active comparator arm, a non-inferiority margin of 3%, a 95%

confidence interval of the effect size and a 90% power, we need to enrol 3000 participants per arm

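### Non-inferiority may be claimed from the full analysis set alone; if intervention-arm participants receive the comparator, an intervention 3 points worse when taken as assigned passes more often than 2.5% of the time

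*Protocol*

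**What the plan says.** Section 4.1 allows phase 3 sub-protocols to test superiority or non-inferiority, and section 4.1.2 makes the comparator in a non-inferiority trial the active treatment. Where a component of standard of care is contraindicated with the study intervention, section 4.1 adds that "we might consider head-to-head comparisons between the study intervention(s) and the SoC component", for superiority or non-inferiority.

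Section 9.1 sets the margin: "we set the default non-inferiority margin at 3% risk difference both for Part A" and for Part B, with the final margin left to the sub-protocol. The decision rule is complete in itself: "Operationally the hypothesis will be evaluated by the two-sided 95% confidence interval with non-inferiority claimed if the interval excludes a 3% difference"; the direction meant is an intervention that does worse than its comparator.

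Section 9.2 defines a full analysis set and a safety set, and no per-protocol set. It defines two sets of data points: DPS1 keeps every observation, and DPS2 drops observations made after discontinuation of study intervention or after rescue. It then states: "Full analysis set and DPS1 are used to estimate the primary endpoints and the secondary endpoints for secondary core objective". The full analysis set with DPS2 serves sensitivity analyses. Neither section separates superiority from non-inferiority on this point.

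The non-inferiority sample size in section 9.5.1 is derived "assuming a 15% primary endpoint rate (progression in Part A and mortality in part B) in the active comparator arm". It uses the 3% margin and a 95% level: "confidence interval of the effect size and a 90% power, we need to enrol 3000 participants per arm".

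**The concern.** In a superiority trial, receipt of the other arm's treatment dilutes the observed difference and works against a claim, so analysing all randomised participants is usually conservative. In a non-inferiority trial the same dilution works towards a claim. If intervention-arm participants receive the comparator and gain its lower risk, the observed difference moves towards zero while the margin stays at 3 points.

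At stake is what a non-inferiority claim from this platform would mean. If the question is whether the intervention, taken as assigned, is less than 3 points worse than the comparator, one interval on the full analysis set with DPS1 does not hold the error at 2.5% once participants cross to the comparator. DPS2 does not repair this. It does not enter the claim, and for progression or death it discards events that occur after discontinuation, which are unlikely to be unrelated to prognosis.

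**Working it through.** **Inputs**
- Decision rule: two-sided 95% interval, that is 2.5% one-sided (9.1).
- Margin: 0.03 (9.1, default).
- Comparator risk: 0.15 (9.5.1).
- Size: 3000 per arm with 90% power (9.5.1), equal allocation (6.3).
- Share s of the intervention arm that receives the comparator: not in the protocol, so assumed and shown as a range.

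**Step 1. Reproduce the planned size**, true difference zero:

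n per arm = 2 × 0.15 × 0.85 × (1.96 + 1.2816)² / 0.03² = 0.255 × 10.508 / 0.0009 ≈ 2977, or 2978 rounded up, against 3000 stated.

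Power at 3000 = Φ(0.03 / √(0.255/3000) − 1.96) = 90.2%. A one-sided 5% level would need only 2427, so the planned size rests on 2.5%.

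**Step 2. False-claim rate at the margin.** Take the intervention risk as 0.18 when taken as assigned, so the true difference is exactly 0.03. Let a random share s switch at the start and take on the full comparator risk:

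- intervention-arm risk p = 0.18 − 0.03s
- expected observed difference = 0.03(1 − s)
- SE = √(p(1 − p)/3000 + 0.15 × 0.85/3000)
- P(claim) = Φ(0.03s/SE − 1.96)

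For s = 10%: p = 0.177, difference 0.027, SE = √(0.1457/3000 + 0.1275/3000) = 0.00954, and P = Φ(0.003/0.00954 − 1.96) = Φ(−1.646) = 5.0%.

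| Share switching | Expected difference | False-claim rate |
|---|---|---|
| 0% | 3.00 points | 2.5% |
| 1% | 2.97 | 2.7% |
| 2% | 2.94 | 2.9% |
| 5% | 2.85 | 3.6% |
| 10% | 2.70 | 5.0% |
| 20% | 2.40 | 9.2% |

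A simulation of 400,000 trials at each of 0, 2, 5, 10 and 20% agrees (2.5, 2.9, 3.5, 5.0 and 9.2%).

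**Step 3. Milder switching.** If switchers regain only half the difference, p = 0.18 − 0.015s. The rate is 3.0% at 5% switching, 3.6% at 10% and 5.0% at 20%.

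**Step 4. Participants who take neither drug.** Assume for illustration an untreated risk of 20% and that 10% of the intervention arm takes nothing. Then p = 0.9 × 0.18 + 0.1 × 0.20 = 0.182, the difference is 3.2 points, and P(claim) = Φ((0.030 − 0.032)/0.0096 − 1.96) ≈ 1.5%, below 2.5%. Only receipt of the comparator dilutes in the way described.

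**Step 5. Power of a second, per-protocol analysis.** If 10% are excluded, 2700 per arm remain: Φ(0.03 / √(0.255/2700) − 1.96) = Φ(1.127) = 87.0%.

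**The case against.** **The primary analysis has a coherent target.** All randomised participants, analysed as allocated with all observed data, estimate the treatment-policy effect. For that effect the error stays at 2.5% whatever the switching. This stands. A reader might infer that the plan's type I error is inflated outright; it is not. The inflation concerns the effect of the treatments taken as assigned.

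**Switching may be uncommon.** A reader might infer from section 4.1 that switching is likely because the comparator can be a component of standard of care. The section does not support that. It foresees head-to-head comparison where the component is contraindicated with the intervention, so a participant would first have to stop the intervention. Section 7.1 describes permanent discontinuation as rare, and section 6.4 has treatment given under supervision with deviations recorded. The phase 2 sample size in 9.5.2 allows for 10% stopping treatment before day 5, but that is discontinuation in another setting, not a switching rate. This stands: the 5–20% rows are assumptions, and 1–2% sits closer to the protocol's own description.

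**The calculation leans high.** It assumes switching at the start, at random, with full benefit. Switching after the endpoint cannot dilute it; in Part A, comparator treatment given because of progression comes too late to matter. Step 3 shows the milder case.

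**A per-protocol set has its own bias.** It selects on events after randomisation. If deteriorating intervention-arm participants receive the comparator and are excluded, likely events leave that arm and the set favours a claim. This limits the safeguard without making it harmful: requiring both analyses can never yield more claims than the full analysis set alone.

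**Detail may follow elsewhere.** Section 9 is a summary, and sub-protocols add specifics. But the claim rule and its analysis set are stated here, and for non-inferiority section 9.1 expressly defers only the final margin.

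**Conclusion.** The point holds as a low-cost improvement to the default non-inferiority framework. As written, 9.1 and 9.2 let non-inferiority be claimed from the full analysis set with DPS1 alone, exactly as for superiority, with no second analysis tied to the claim. For an intervention 3 points worse when taken as assigned, the false-claim rate rises from 2.5% to 2.7–2.9% at 1–2% switching to the comparator, 3.6% at 5%, 5.0% at 10% and 9.2% at 20%.

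These figures rest on 3000 per arm, a 15% comparator risk and random switching at the start with full gain of the comparator risk; with half the gain, 10% switching gives 3.6%. The protocol supplies no switching rate.

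A reader might also infer that every participant who fails to take the allocated drug pulls the arms together. That does not follow, because those who take neither drug may push the difference the other way. The only sub-protocol synopsis in the document (10.8.1) is placebo-controlled and sized as a superiority trial, so the point concerns future non-inferiority sub-protocols, not that trial.

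**What to change.** For non-inferiority sub-protocols only:

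- In 9.2, define a per-protocol set: participants who received their allocated drug and did not receive the other arm's drug before the endpoint, with endpoints still followed to day 14 (Part A) or day 60 (Part B).
- In 9.1, state that non-inferiority is claimed only if the two-sided 95% interval excludes the margin in both the full analysis set with DPS1 and the per-protocol set.
- Say that the per-protocol set supplements the full analysis set and does not replace it, because it selects on post-randomisation events.
- In 9.5.1, restate the power: at most about 87% in place of 90% if 10% fall outside the per-protocol set (2700 per arm).

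The cost is a few lines of text, one further analysis and the restated power. No extra patients are needed, and superiority trials are unchanged.

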9.3. Statistical Analyses

9.3.1. General considerations

All continuous variables will be summarized using the following descriptive statistics: n (non-missing sample size), mean, standard deviation (SD), 1st quartile, median, 3rd quartile, maximum and minimum. The frequency and percentages (based on the non-missing sample size) of observed levels will be reported for all categorical variables.

The number of participants and the flowchart of the study will be presented. The period of enrolment and the total number of participants screened to be included in the study will be presented. The number of ineligible participants and the total number of randomized participants will be presented. The number of participants who never receive the study intervention will also be presented by treatment group and those who were included in the full analysis set and the safety analysis set will be presented.

Baseline is considered as the day 1 visit and the baseline data is data collected just before intervention at day 1.

For all outcomes, comparisons will be made between each study intervention group and the control group. The comparisons between each study intervention and the control group will be tested using Fisher's exact test or Pearson chi-square test for categorical variables and Man-Whitney test for continuous variables. All p-values are two-sided with a significant level set at 0.05.

9.3.2. Primary endpoint(s) analysis

The primary endpoint for Part A is the occurrence of disease progression, defined as a progression of disease state from moderate (WHO scores 4-5) to severe/critical (WHO score 6-9) or death within 14 days, and the primary endpoint for Part B is the occurrence of death within 60 days. The Kaplan-Meier estimate will be used to estimate the disease progression rates. Kaplan-Meier curves will be plotted for the primary endpoints. We will calculate the Cochran-Mantel-Haenszel treatment difference and the 95% associated confidence interval in

the percentage of participants with disease progression (i.e., study intervention group response rate minus control group response rate) adjusted for the stratification factors of the randomization. The analyses may also be adjusted for other prognostic factors as sensitivity analyses. If the primary analysis adjusted for centre becomes unstable or non-identifiable due to small strata, adjustment by country will be done instead. The effect of study intervention will also be assessed using a time-to-event regression model with treatment group and adjustments for stratification factors.

The validity of the proportionality assumption will be evaluated and tested. Efforts to minimize lost to follow-up will be considerable. However, small amounts of missing data may occur. In such cases, participants without final outcome data will be censored at the date of last information. Sensitivity analyses will be conducted assuming all participants lost to follow-up progressed in both arms at time of censoring (worst case imputation), or none progressed and did not meet the primary endpoint (best case imputation). These sensitivity analyses will be fully defined in the statistical analysis plan (SAP).

